## 6 STUDY OBJECTIVES AND ENDPOINTS

### 6.1 Study Objectives

#### 6.1.1 Primary Objective

To assess the long-term durability of response over a 24-week period following withdrawal of nemolizumab in subjects with PN who previously responded to treatment in the LTE study RD.06.SPR.202699

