**Table 8. Estimand of Primary Endpoint**

Treatment	Population	Endpoint	Intercurrent events	Summary measure
Randomized treatment with subcutaneous injections of nemolizumab or placebo at Week 0, 4, 8, 12, 16 and 20	All randomized subjects (intent-to-treat population)	Time to relapse meeting at least 1 of the defined criteria	Time to relapse will be censored at the last observation prior to treatment discontinuation or use of prohibited medication	Hazard ratio of nemolizumab and placebo

As the primary analysis, the time to relapse will be analyzed using Cox proportional hazard model with treatment group, dosing regimen as a factor, and baseline PP NRS score and IGA score as covariates. The estimated hazard ratio and the corresponding 95% CI will be presented. If the assumption of proportionality is not met, other appropriate methods will be used and documented in the SAP.

In addition, Kaplan-Meier survival plots will be presented for time to relapse. The median time, 25th and 75th percentiles, and the corresponding CI will be reported.

If a subject withdraws from the study, takes prohibited medication, or completes the study without any relapse, time to relapse response will be censored respectively at the time of the last efficacy assessment (PP NRS and IGA) prior to study withdrawal, use of prohibited medication, or the completion of the study. If a subject has no efficacy assessment after randomization, then time to relapse will be censored at Day 1.

For the purpose of efficacy analysis, subjects receiving any prohibited therapies will be censored from the primary analysis.

As a supporting analysis, the time to relapse will also be analyzed using the same methods in the per-protocol population.

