4.6. Study Procedures and Flowchart

See [Table 4-1](#) for study procedures.

This document is confidential.

Table 4-1: Schedule of Assessments

	Baseline ^a	Treatment Period						FU	ET	Unscheduled
Visit	V1	V2	V3	V4	V5	V6	V7	V8		
Week	W0 (Day 1)	W4	W8	W12	W16	W20	W24	W32	if applicable ^b	if applicable ^c
Visit Window (days)		±1	±3	±3	±3	±5	±5	±7		
ICF ^a	X									
Inclusion/exclusion	X									
Demographics	X									
Medical history, previous therapies and procedures, smoking status	X									
Patient-Reported Outcomes										
PP NRS/ SD NRS ^{d, e}	X							X	(X)	
DLQI ^e	X				X		X	X	(X)	
Efficacy Assessments										
IGA	X	X	X	X	X	X	X	X	(X)	
Safety Assessments										
ACT ^{e, f}	X	X	X	X	X	X	X	X	(X)	
Respiratory examination	X	X ^g	X ^g	X	X ^g	X ^g	X	X	(X)	
PEF testing	X	X ^g	X ^g	X	X ^g	X ^g	X	X	(X)	
Vital signs ^h	X	X	X	X	X	X	X	X	(X)	
Full physical examination	X			X			X	X	(X)	
Symptom-directed physical examination		X	X		X	X				
Height	X								(X)	
Weight	X					X		X	(X)	
12-lead ECG ⁱ	X					X		X	(X)	
Contraceptive counseling	X								(X)	
Adverse events ^e	X	X	X	X	X	X	X	X	(X)	
Concomitant therapies and procedures ^e	X	X	X	X	X	X	X	X	(X)	
Laboratory Assessments										
Blood samples for hematology and clinical chemistry ^j	X			X			X	X		(X)
Urinalysis	X			X			X	X		(X)
Urine pregnancy test ^k	X	X	X	X	X	X	X	X	(X)	

This document is confidential.

	Baseline ^a	Treatment Period							FU	ET	Unscheduled
Visit	V1	V2	V3	V4	V5	V6	V7	V8			
Week	W0 (Day 1)	W4	W8	W12	W16	W20	W24	W32		if applicable ^b	if applicable ^c
Visit Window (days)		±1	±3	±3	±3	±5	±5	±7			
FSH ⁱ	X									(X)	
Blood sample for virology (HIV, Hepatitis B and C)										(X)	
Blood sample for TB test										(X)	
POE & Immunogenicity Assessments											
Blood sample for POE ^{c, m}	X							X		X	(X)
Blood sample for ADA ^{c, m}	X							X		X	(X)
Study Drug Administration											
Randomization	X										
Study drug injection ^{n, o, p, q, r}	X	X	X	X	X	X				(X)	

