10.1. Primary Efficacy Endpoints

10.1.1. Primary Analysis of Primary Efficacy Endpoint

The primary endpoint is the time to relapse which is defined as meeting at least 1 of the following criteria:

- Increase in (weekly average of the) PP NRS score ≥ 4 points from baseline
- Increase in IGA score ≥ 2 points from baseline;

For primary endpoint, any subjects with missing data for PP NRS and IGA Score both at visit will be censored at the respective timepoint. If any one of PP NRS or IGA Score data is available for the visit, calculation for primary endpoint will be made using available results. If a subject has taken prohibited medication at any point of time during treatment period, then subject will be censored at the respective visit.

The primary endpoint will be analyzed using Cox proportional hazard model with treatment group, dosing regimen as a factor, and baseline PP NRS score and IGA score as covariates on ITT population. The estimated hazard ratio and the corresponding 95% CI will be presented. A supportive analysis also will be performed using Per-Protocol Population.

Kaplan-Meier survival plots will also be presented for time to relapse. The median time, 25th and 75th quantiles along with corresponding CI will be presented using ITT/PP.

Censoring rule for primary endpoint variable is as follows:

Situation	Date of Progression or Censoring	Outcome
Relapse as described	Date of Relapse	Event
Subject withdrawn without relapse	Date of last efficacy assessment (PP NRS and IGA) prior to withdrawal	Censored
Treatment Discontinuation	Date of last efficacy assessment (PP NRS and IGA) prior to Treatment Discontinuation	Censored
Prohibited medication without relapse	Date of last efficacy assessment (PP NRS and IGA) prior to prohibited medication	Censored
Completes the study without relapse	Date of Week 24 completion	Censored
No Efficacy assessment	Date of study Day 1	Censored

This document is confidential.

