10.2.1. Investigator's Global Assessment (IGA)

The IGA is a 5-point scale used by the Investigator or trained designee to evaluate the global severity of PN and the clinical response to a treatment (see [Table 10-1](#)).

Table 10-1: Investigator Global Assessment Scale

0	Clear	No nodules
1	Almost Clear	Rare palpable pruriginous nodules
2	Mild	Few palpable pruriginous nodules
3	Moderate	Many palpable pruriginous nodules
4	Severe	Abundant palpable pruriginous nodules

IGA treatment success is defined as 0 (clear) or 1 (almost clear) on the IGA scale.

IGA will be collected at Baseline/Day 1, Week 4, Week 8, Week 12, Week 16, Week 20, Week 24 and Early Termination or any unscheduled visit. In case of missing assessment at Baseline, the last available assessment prior study drug administration will be considered as Baseline.

IGA will be summarized as a categorical and continuous variable at each analysis visit. Absolute change from Baseline for the IGA score will also be presented in the summary on the ITT and Per-Protocol Population.

The proportion of subjects maintaining IGA success and subjects with increase in IGA ≥ 2 points from baseline will be summarized on the ITT based on OC. The estimate of treatment unadjusted and strata-adjusted differences with the corresponding two-sided 95% confidence intervals, and p-values from the CMH test will be presented.

The analysis will be repeated:

- on Per-Protocol Population, based on OC
- on ITT population, imputing missing values with non-responder imputation

Line plot for proportion of subjects maintaining IGA success and proportion of subjects with increase in IGA ≥ 2 points from baseline, both using non-responder imputation, will be for the ITT Population.

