20.1. Example SAS Code

1. The Example SAS code for Time to Event and Hazard Ratio

```
proc lifetest data=analysis_data;
  time aval*cnsr(1);
  strata trtp;
run;

proc phreg data=analysis_data;
  class trtp stratum;
  model aval*cnsr(1)=trtp stratum;
run;
```

2. The example SAS code for CMH model is listed as below:

```
proc freq data=analysis_data;
  tables stratum*trt*resp/ cmh alpha=0.1;
run;
```

3. The example SAS code for MMRM model is listed as below:

```
proc mixed data = analysis_data;
  class stratum trtp avisit subjid;
  model chg = base stratum trtp avisit trtp*avisit/ ddfm=kr;
  repeated avisit / subject=subjid(trtp) type=un;
  lsmeans trtp/ cl diff;
  lsmeans trtp*avisit/ slice=avisit cl diff;
run;
```

4. The example SAS code for ANCOVA model is listed as below:

```
proc mixed data = analysis_data;
  class stratum trtp;
  model chg = base stratum trtp;
```

This document is confidential.

lsmeans trtp/ cl diff;

run;

This document is confidential.

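### Censoring completers on their own Week 24 visit date inflates the tail of the Kaplan-Meier relapse curve; the primary hazard ratio is essentially unaffected

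*SAP*

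**What the plan says.** The table in SAP 10.1.1 gives an event the "Date of Relapse" and a subject who finishes without relapse the "Date of Week 24 completion". The protocol (14.3.1) censors at the last efficacy assessment "prior to study withdrawal, use of prohibited medication, or the completion of the study", which for a completer leads to essentially the same date.

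The IGA half of the relapse definition is observed only in clinic: "IGA will be collected at Baseline/Day 1, Week 4, Week 8, Week 12, Week 16, Week 20, Week 24 and Early Termination", or at an unscheduled visit. The schedule (Protocol Table 7, SAP Table 4-1) allows 5 days either side for the Week 24 visit. The Week 24 analysis windows are wider: Days 155 to 210 for IGA (SAP Table 8-1) and Days 162 to 175 for the evening diary (SAP Table 8-2). SAP 8.4 introduces its windows for by-visit summaries and does not apply them to time to relapse.

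For the Kaplan-Meier output the SAP states: "The median time, 25th and 75th quantiles along with corresponding CI will be presented using ITT/PP". It names no Week 24 percentage. The example code in SAP 20.1 is a plain product-limit analysis, with no nominal time scale, truncation or interval-censored method.

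**The concern.** At Week 24, passing the visit and being censored are the same act. A subject found relapse-free on Day 165 is gone from the denominator when another subject's Week 24 relapse is dated Day 173. Censoring then depends on appointment scheduling, and each later relapse is divided by whoever was booked later still. Earlier visits do not have this problem for completers, because passing them censors nobody.

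The primary objective is "To assess the long-term durability of response over a 24-week period following withdrawal of nemolizumab", and Protocol 7.2 says this durability is to be read in the placebo arm. A hazard ratio does not show how long response lasts; the placebo curve and its quantiles do. With no Week 24 percentage planned, readers will take one from the end of the curve, which is the affected part. The sensitivity analyses in SAP 10.1.2 state no different dating rule.

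**Working it through.** **Inputs from the documents.** Week 24 target day: 24 × 7 + 1 = 169; window 169 ± 5 = Days 164 to 174. Arm size: about 20 (40 randomized 1:1; SAP 4.3, Protocol 14.1). SAP 4.1 says about 100, so 50 per arm is also shown. The documents give no relapse rates, visit-date distribution or share of relapses dated at visits; these are assumed below.

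**Reference value.** With no dropout, everyone without an earlier relapse is assessed at Week 24, so the correct Week 24 relapse percentage is the crude proportion.

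**Worked example.** Take 20 subjects, 4 relapsed earlier, 16 seen at Week 24 and 1 of those in relapse. Crude: 5/20 = 25%. The curve stands at 16/20 = 0.80 before Day 164. If r subjects are still at risk on the day of the last relapse,

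KM relapse = 1 − 0.80 × (1 − 1/r).

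Suppose 8 are seen on Days 164–168, 5 on Days 169–171, and one each on Days 172, 173 and 174:

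| Day of the Week 24 relapse | r | KM relapse |
|---|---|---|
| 164 | 16 | 25% |
| 169 | 8 | 30% |
| 172 | 3 | 46.7% |
| 173 | 2 | 60% |
| 174 | 1 | 100% |

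The data are the same in every row; only the appointment date differs.

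**Simulation 1.** 20 per arm, 3,000 replicates, visit days uniform within the scheduled windows, no dropout, constant relapse risk h per 4-week interval, so expected relapse is 1 − (1 − h)^6: 11.4%, 26.5% and 46.9% for h = 2%, 5% and 10%. Crude proportion against mean final KM:

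| h | All relapses visit-dated | Half visit-dated |
|---|---|---|
| 2% | 11.4% → 14.8% | 11.4% → 13.1% |
| 5% | 26.6% → 32.9% | 26.4% → 29.9% |
| 10% | 46.7% → 54.8% | 46.6% → 51.0% |

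The inflation is 3.4, 6.3 and 8.1 points when all are visit-dated, and 1.7, 3.5 and 4.4 when half are; a repeat run put the last figure at about 5. At h = 10% with all visit-dated, the SD of the final estimate is 17 points, against 11 on nominal days. The curve reached 50% when fewer than half had relapsed in 1 to 13% of arms, and fell falsely to 100% relapse in about 1 to 6%.

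**Simulation 2.** 8,000 arms per scenario, uniform Week 24 days, fixing the percentage relapsed before Week 24 and the percentage of the remainder found in relapse at that visit. With 20 per arm: (10%, 3%) 12.8% → 17.5%; (20%, 5%) 24.0% → 30.4%; (20%, 10%) 28.1% → 39.9%; (40%, 10%) 45.8% → 54.2%. With 50 per arm: (20%, 10%) 27.9% → 41.0%; (40%, 10%) 46.0% → 55.6%. A larger trial does not remove the bias. KM never fell below the crude proportion.

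**Hazard ratio.** Median Cox hazard ratio at assumed risks of 10% against 3% per interval: 0.274 on actual dates and 0.273 on nominal days (20 per arm); 0.286 and 0.285 (50 per arm). Single trials move a little either way (mean absolute change in log hazard ratio 0.03 to 0.12 over the settings tried), but the medians show no shift.

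**After the change.** With Week 24 relapses and completers at one common time and events first, KM equalled the crude proportion in every scenario (for example 28.1% and 28.1%), with no false collapse or false median.

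**The case against.** The estimand's summary measure is the hazard ratio, the primary analysis is a Cox model, and the Kaplan-Meier output is additional. The curve before about Day 164 is correct, so a quantile is wrong only if it is first crossed in the last stretch. This stands, and it limits the severity.

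Peak pruritus is recorded daily and averaged weekly, so many relapses may be dated between visits. This also stands, which is why the half-visit-dated column matters. The documents do not give the share.

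The text is also less firm than a pure calendar-date rule. The relapse date is not defined, the unit of the analysis time is not given, SAP 10.1.1 elsewhere speaks of censoring at a timepoint or visit, and SAP 15.2.5.4 puts visits on the X-axis by default. Coding by nominal visit would remove the problem. However, the censoring table specifies dates, so the plan needs to say so if nominal time is meant.

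Some relief comes from the by-visit proportion with a pruritus increase of at least 4 points, planned through Week 24 on analysis visits. It is free of this artefact, but it is one component and not the composite.

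A reader might infer that the treatment comparison is biased, or that the curves will collapse to 100%. Neither is supported. The hazard ratio is essentially unchanged, and collapse requires that everyone still at risk on the last event day has relapsed.

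**Conclusion.** The concern holds for the tail of the Kaplan-Meier curve and for any median or quartile first crossed there. As written, the rule biases these towards more relapse and adds noise. With 20 per arm the inflation is about 2 to 5 points if half of relapses are visit-dated and 3 to 8 if all are. It can be larger, up to about 12 points in Simulation 2 (39.9 − 28.1 = 11.8), when many relapses are first found at Week 24.

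The size rests on assumed relapse rates, visit scatter and no dropout; the direction does not. The bias needs at least one Week 24 relapse dated after another subject's completion. Same-day ties do no harm, and relapses dated before the first completer is censored are unaffected. Because the primary summary measure survives, this is a should-fix for the descriptive durability estimate and not a threat to the primary comparison.

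**What to change.** Amend the censoring table in SAP 10.1.1 before unblinding:

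- Assign every relapse detected in the Week 24 analysis window (IGA or PP NRS, including any dated after Day 169) and every relapse-free completer to Day 169, with events preceding censorings at ties.
- Use nominal visit days (29, 57, 85, 113, 141) for earlier visit-detected relapses.
- State the date used for a weekly PP NRS relapse, for example the target day of its analysis week. For consistency, put the other censoring rows on the same scale.
- Report the Kaplan-Meier relapse-free percentage at Week 24 with its CI. The median may well not be reached: at an assumed 40% placebo relapse, P(X ≥ 10) for X ~ Bin(20, 0.4) is about 25%.

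Keeping actual dates and censoring all completers at Day 174 is not an equivalent repair, because Week 24 data run to Day 210 (IGA) and Day 175 (PP NRS). A relapse dated after Day 174 would then have no completer left at risk. With an assumed 10% of Week 24 visits on Days 175 to 183, that rule gave more false collapses than the SAP rule: about 11% against 8 to 9% at h = 10%, 7.3% against 3.9% at 5%, and 3.5% against 1.5% at 2%.

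The cost is a few lines in the table and one derivation, with no new data. The downside is that reported times are nominal and not exact days.

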10.1.2. Sensitivity Analyses of Primary Efficacy Endpoint

Sensitivity analyses for primary endpoint will be conducted in order to test for the robustness of the primary analyses. The following sensitivity analyses will be conducted:

- Same analysis on Per-Protocol Population as mentioned in 10.1.1.
- 'Actual strata of randomization' instead of 'stratum at the randomization' for subjects stratified incorrectly.
- Removal of COVID-19 affected visits (i.e. exclusion of subjects from visit, if visit was missed due to COVID-19.) This analysis will be performed only if >2% subjects have missing data due to COVID-19.

10.2. Secondary Efficacy Endpoints

The following secondary endpoints are to be analysed at the scheduled visits:

Endpoint	Analysis Visit	Analysis to be done on which Population	Statistical Tests
Proportion of subjects maintaining IGA success at each scheduled visit	Baseline, Week 4, Week 8, Week 12, Week 16, Week 20, Week 24	On the ITT and Per-Protocol Population	CMH
Proportion of subjects with increase in IGA ≥ 2 points from baseline at each scheduled visit	Baseline, Week 4, Week 8, Week 12, Week 16	On the ITT and Per-Protocol Population	CMH
Proportion of subjects with increase in PP NRS score ≥ 4 points from baseline at each scheduled visit	Baseline, Week 4, Week 8, Week 12, Week 16, Week 20, Week 24	On the ITT and Per-Protocol Population	CMH
Absolute and percent change from baseline in PP NRS at each scheduled visit	Baseline, Week 4, Week 8, Week 12, Week 16, Week 20, Week 24	On the ITT and Per-Protocol Population	ANCOVA
Absolute and percent change from baseline in PP NRS at each scheduled visit	Baseline, Week 4, Week 8, Week 12, Week 16, Week 20, Week 24	On the ITT	MMRM

This document is confidential.

Endpoint	Analysis Visit	Analysis to be done on which Population	Statistical Tests
Absolute and percent change from baseline in SD NRS at each scheduled visit	Baseline, Week 4, Week 8, Week 12, Week 16, Week 20, Week 24	On the ITT and Per-Protocol Population	ANCOVA
Absolute and percent change from baseline in SD NRS at each scheduled visit	Baseline, Week 4, Week 8, Week 12, Week 16, Week 20, Week 24	On the ITT	MMRM
Change from baseline in DLQI at each visit	Baseline, Week 16, Week 24	On the ITT Population	ANCOVA

Abbreviations: CMH=Cochran-Mantel-Haenszel; DLQI=Dermatology Life Quality Index; IGA=Investigator Global Assessment; PP=Peak Pruritus; SD=Sleep Disturbance.

Binary secondary efficacy endpoints will be analyzed using a Cochran-Mantel-Haenszel test adjusted for dosing regimen based on OC and imputation with missing efficacy response considered as the non-responder (i.e., IGA success) and missing relapse response considered as a relapse (i.e., increase in PP NRS or IGA). The estimate of treatment unadjusted and strata-adjusted differences with the corresponding two-sided 95% confidence intervals, and p-values from the CMH test will be presented.

Continuous secondary endpoints will be analyzed using analysis of covariance (ANCOVA) based on OC with treatment group and dose regimen as factors, and baseline value as the covariate. In addition, for PPNRS and SDNRS endpoints, the mixed effect model for repeated measure (MMRM) approach based analysis will be repeated on OC, including treatment group and dose regimen as factor, visit, interaction term between treatment and visit along with corresponding baseline value as independent covariate. Kenward-Roger approximation is used to estimate denominator degrees of freedom. An unstructured covariance is used to model the within-patient errors in the analysis. While applying the model, if convergence criteria not met with unstructured covariance matrix, then "Type = CS or type =ar(1)" covariance matrix will be applied to achieve convergence of the model. The matrix with the minimum AIC criteria will be selected for the further analysis. For both analyses, the least squares means, estimated standard error, and 95% confidence interval (CI) for each endpoint will be presented for each treatment group and analysis visit; the estimated treatment difference for each endpoint at each analysis visit will be summarized by presenting the difference in least squares means between treatment groups, the two-sided 95% CI, and associated p-value as well.

All secondary endpoints will be presented descriptively using OC.

This document is confidential.

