#### 6.2.2 Secondary Endpoints

##### 6.2.2.1 Efficacy Endpoints

The secondary efficacy endpoints include:

- Proportion of subjects with increase in PP NRS score  $\geq 4$  points from baseline at each scheduled visit

This document is confidential.

- Proportion of subjects maintaining IGA success, defined as IGA score of 0 (clear) or 1 (almost clear) at each scheduled visit
- Proportion of subjects with increase in IGA  $\geq 2$  points from baseline at each scheduled visit
- Absolute and percent change from baseline in PP NRS at each scheduled visit
- Absolute and percent change from baseline in Sleep Disturbance Numeric Rating Scale (SD NRS) at each scheduled visit
- Change from baseline in DLQI at Week 16 and Week 24

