## 14 STATISTICAL ANALYSIS

A statistical analysis plan (SAP) will be prepared after the protocol is approved. This document will provide further details regarding the definition of analysis variables and analysis methodology to address all study objectives. The SAP will serve as a compliment to the protocol and supersedes it in case of differences.

The statistical evaluation will be performed using SAS® software version 9.4 or higher (SAS Institute, Cary, NC). All data will be listed. All primary and secondary efficacy endpoints, and safety endpoints will be summarized. Summary statistics will be presented by treatment group and dose regimen. For continuous variables, data will be summarized with the number of subjects (N), mean, standard deviation, median, minimum, and maximum by treatment group and dosing regimen. For categorical variables, data will be tabulated with the number and proportion of subjects for each category by treatment group and dosing regimen. For time-to-event, data will be summarized using Kaplan-Meier method.

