If a subject meets the criteria for relapse at any point, the subject will exit the study and re-enter the LTE study (see [Figure 4-1](#)). Subjects who exit the study before Week 24 should complete an early termination (ET) visit. Subjects who complete the study through Week 24 are eligible to re-enroll in the LTE study.

Subjects who prematurely discontinue study drug for reasons other than relapse will be encouraged to complete the scheduled study visits. These subjects will only be eligible for re-enrollment in the LTE study if they continue with study visits through Week 24.

Subjects who discontinue the study for reasons other than relapse before Week 24 or who will not continue nemolizumab treatment in the LTE study should complete a follow-up visit, 12 weeks (± 7 days) after the last study drug injection.

[figure not shown]
Follow-up Period

This document is confidential.

A follow-up visit will be conducted 8 weeks (± 7 days) after completing the treatment period and/or 12 weeks (± 7 days) after the last study drug injection for all subjects who will not continue nemolizumab treatment in the LTE study. Twelve weeks corresponds to approximately 5 half-lives of nemolizumab when administered subcutaneously Q4W at the doses used in this study.

An overview of the study is presented in [Figure 4-2](#).

Figure 4-2: Study Design

*Clinical responder is defined as a subject with an Investigator Global Assessment (IGA) score= 0 or 1 and improvement in Peak Pruritus Numeric Rating Scale (PP NRS) score of ≥ 4 points from baseline of the lead-in study at Week 52 visit of the LTE study. Note: Lead-in study baseline is defined as baseline PP NRS score in the Phase 3 studies RD.06.SPR.202685 or RD.06.SPR.203065 for subjects who rolled over into the LTE from these studies. For subjects who entered the LTE study from the Phase 2 study RD.03.SPR.115828, the baseline PP NRS score at entry into the LTE study RD.06.SPR.202699 will be used.

** Relapse is defined as an increase in weekly average of PP NRS score ≥ 4 points from baseline or an

This document is confidential.

increase in IGA score ≥ 2 from baseline at any point during the study. Subjects who relapse at any point during the treatment period or who complete through Week 24 are eligible for LTE re-entry.

Abbreviations: BL = baseline; LTE = long-term extension; R = randomization; W = week.

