ACT = Asthma Control Test; ADA = anti-drug antibody; AE = adverse event; DLQI = Dermatology Life Quality Index; ECG = electrocardiogram; ET = early termination; FSH = follicle-stimulating hormone; FU = follow-up; HIV = human immunodeficiency virus; ICF = informed consent form; IGA = Investigator Global Assessment; LTE = long-term extension; PEF = peak expiratory flow; POE = proof of exposure; PP NRS= peak pruritus numeric rating scale; SD NRS= sleep disturbance numeric rating scale; TB = tuberculosis; UPT = urine pregnancy test; V = visit; W = week.

- After signing the ICF, all subjects will be evaluated for study participation, based on eligibility criteria. The Week 52 study assessments from the LTE lead-in study RD.06.SPR.202699 will be used as baseline assessments for the current study.
- Subjects who relapse or discontinue prematurely (before the Week 24 visit) should complete an ET visit. If the subject discontinues for reasons other than relapse before Week 24, or will not continue with nemolizumab treatment in the LTE study, a follow-up visit should also be completed, 12 weeks (±7 days) after the last study drug injection.
- Assessments to be conducted at the unscheduled visit depend on the reason for the visit. POE and ADA analyses should only be performed at unscheduled visits that are conducted for safety reasons when safety labs are collected for the management/monitoring of an AE. When a series of unscheduled visits is needed for the monitoring of the same AE, the POE and ADA collection is not required if already done at the first unscheduled visit of the series. Additional collection of samples for POE and ADA analysis should be performed per Investigator's judgment.
- PP NRS to be recorded by subjects once daily in the evening. SD NRS to be recorded by subjects once daily in the morning and if possible, within 1 hour of getting out of bed.
- Patient-reported outcome assessments and designated safety measurements (including AE and concomitant therapies/procedures assessments) should occur before Investigator assessments, laboratory sample collections, and study drug administration.
- Subjects with a history of asthma will complete the ACT testing at all visits. Subjects with a new (de novo) diagnosis of asthma will complete the ACT testing beginning from de novo diagnosis and at all subsequent scheduled visits.

This document is confidential.

Statistical Analysis Plan for Interventional Studies

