5.2. Secondary Efficacy Endpoints

The secondary efficacy endpoints are as follows:

- Proportion of subjects with increase in PP NRS score ≥ 4 points from baseline at each scheduled visit
- Proportion of subjects maintaining IGA success, defined as IGA score of 0 (clear) or 1 (almost clear) at each scheduled visit
- Proportion of subjects with increase in IGA ≥ 2 points from baseline at each scheduled visit
- Absolute and percent change from baseline in PP NRS at each scheduled visit
- Absolute and percent change from baseline in Sleep Disturbance Numeric Rating Scale (SD NRS) at each scheduled visit
- Change from baseline in DLQI at Week 16 and Week 24

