13.6.3. Peak Expiratory Flow

Peak expiratory flow (PEF) testing during the clinical study will be performed under the supervision of qualified study personnel. Peak expiratory flow measurements should consist of 3 good efforts, with the best result documented. Obtained PEF values will be compared to predicted values based on the subject's age, sex and height.

PEF testing will be performed for all subjects at Baseline/Day 1, Week 12, Week 24, Early Termination, and Week32/Follow-up visits. For subjects reporting a medical history of asthma, PEF testing will be performed at all visits during the clinical study. For subjects diagnosed with new (de novo) asthma, PEF testing will be performed at all visits, starting with the visit in which the diagnosis was confirmed.

Following PEF parameters will be summarized as a continuous variable (Baseline and scheduled visits only):

- Actual peak expiratory flow rate
- Predicted peak expiratory flow rate
- Actual PEF of predicted value (%).

These PEF parameters will be summarized separately for the subset of subjects with and without history of asthma.

The number and percentage of subjects with PEF < 80% will be summarized by treatment group, visit (baseline and scheduled visits only), and medical history of asthma (with and without history of asthma).

All PEF results will be listed on the Safety population.

This document is confidential.

14. Changes from Analysis Planned in Protocol

- Summary Statistics will be presented by Treatment Group instead of “by Treatment Group and dosing regimen”.

This document is confidential.

15. Programming Considerations

All TFLs and statistical analyses will be generated using SAS® 9.4 or higher (SAS® Institute Inc., Cary, NC, USA) on a SAS Server. Changes to the software version (e.g. upgrades), or use of additional software consistent with the SAP will not be considered a violation of the SAP.

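### The SAP 10.2 row for the IGA-worsening endpoint stops at Week 16, although the endpoint is defined at every scheduled visit and IGA is collected to Week 24

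*SAP*

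**What the plan says.** SAP 5.2 lists as a secondary efficacy endpoint: "Proportion of subjects with increase in IGA ≥ 2 points from baseline at each scheduled visit". Protocol 6.2.2.1 defines it in the same way, ending "points from baseline at each scheduled visit", and protocol 14.3.2 repeats the by-visit definition where it specifies the test.

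The SAP 10.2 table then assigns each secondary endpoint its analysis visits, population and test. For this endpoint the visit cell reads "Baseline, Week 4, Week 8, Week 12, Week 16" and stops. The same string opens the longer lists in neighbouring rows, but here it is the full cell, followed directly by the population (ITT and per-protocol) and the test (CMH).

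On data collection, SAP 10.2.1 says "IGA will be collected at Baseline/Day 1, Week 4, Week 8, Week 12, Week 16, Week 20, Week 24 and Early Termination", with unscheduled visits added. SAP Section 14, which records departures from the protocol, has a single entry, beginning "Summary Statistics will be presented by Treatment Group instead of"; it concerns how summaries are displayed. Protocol Section 14 says that the SAP "supersedes it in case of differences".

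**The concern.** The row contradicts its own title. The 10.2 table is the place a programmer would go for the visits to test, and the titles in the SAP's table and figure indexes for this endpoint set no week limit that would correct it. The protocol cannot be relied on to settle the matter, because it gives way to the SAP where the two differ.

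At stake is one of the two IGA-based secondary endpoints in a study whose primary objective is durability over 24 weeks. Without Weeks 20 and 24, it has no planned test in the last part of that period. If the gap were noticed only after unblinding, deciding whether to include those visits would be a post-hoc choice that is easily avoided now.

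**Working it through.** No modelling is needed. The check sets the visit lists side by side.

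| Source | Post-baseline visits for IGA or the endpoint |
|---|---|
| SAP 10.2, row for IGA increase of at least 2 points | Weeks 4, 8, 12, 16 |
| Title of that row; lead-in to the 10.2 table; SAP 5.2; protocol 6.2.2.1 and 14.3.2 | every scheduled visit |
| SAP 10.2.1 and the schedules of assessments (IGA collection) | Weeks 4, 8, 12, 16, 20, 24 |
| SAP Table 8-1 (IGA windows) | Weeks 4 to 24; Week 20 is days 127 to 154, Week 24 is days 155 to 210 |
| SAP 10.2, row for maintained IGA success | Weeks 4, 8, 12, 16, 20, 24 |
| SAP 10.2, row for PP NRS increase of at least 4 points | Weeks 4, 8, 12, 16, 20, 24 |

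**Count.** Six visits are scheduled and four are listed: 6 − 4 = 2 are missing, and 2/6 = 33%.

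**Data left without a listed visit.** The Week 16 IGA window ends on day 126. IGA values from day 127 to day 210 therefore fall in windows that the row does not name. SAP 8.4 also places early-termination and unscheduled assessments in these windows, so an IGA worsening first seen at an exit visit after day 126 would enter no listed test of this endpoint.

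**Tests affected.** The table index plans three CMH analyses of the endpoint: observed cases in ITT, observed cases in the per-protocol population, and imputed in ITT (Tables 14.2.2.1.9 to 14.2.2.1.11). At six visits that is 3 × 6 = 18 by-visit comparisons. The row as written gives 3 × 4 = 12, so 6 are lost.

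**Could the stop be deliberate?** SAP 10.2, 10.2.1 and Section 14 give no reason for it. Maintained IGA success uses the same score from the same visits and runs to Week 24. The PP NRS and SD NRS change rows also run to Week 24. The DLQI row is shorter (Weeks 16 and 24), but that matches its own definition.

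**Could it be a fault of text extraction?** Unlikely. The cell is followed by an intact population column and test, and the neighbouring rows are complete.

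**The case against.** The best defence is that the SAP as a whole already makes the intention clear. The conflict lies inside the SAP: the row title, the table's lead-in and SAP 5.2 agree with the protocol. The opening of SAP Section 10 has all efficacy variables summarised at each analysis visit, and Table 8-1 makes Weeks 20 and 24 IGA analysis visits. This stands as far as it goes. A reader might infer from the precedence rule that the SAP has formally cut the endpoint at Week 16. The documents do not support that, because the SAP's own definition was not changed. The defence does not remove the contradiction in the cell that assigns the test, however, and a general statement about summaries does not specify a CMH test.

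Two stronger readings are tempting.

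- **That the planned analyses of the worsening endpoints are themselves in error.** Relapsers leave: "If a subject meets the criteria for relapse at any point, the subject will exit the study and re-enter the LTE study". Later observed-case comparisons therefore rest largely on subjects who have not relapsed, while missing-as-relapse counts an exit on one criterion as a relapse on the other. A reader might conclude that one estimate is too small, the other too large, and a third analysis is required. But the endpoint is a proportion at each visit; time to first relapse is the primary endpoint. Both analyses are prespecified in the protocol and the SAP. The exit assessment is also not lost: "Subjects who relapse or discontinue prematurely (before the Week 24 visit) should complete an ET visit", and SAP 8.4 windows that visit. Carrying the exit status forward would have its own bias, because it treats a subject who left on one criterion as never meeting the other. Any size given to the discrepancy would need relapse rates, and the share of relapses meeting each criterion in each arm, none of which the documents give. A further analysis is a matter of preference.
- **That the non-responder label reverses the imputation.** The label in SAP 10.2.1, 10.2.2 and the output titles is awkward for a worsening endpoint. The direction is fixed elsewhere: SAP 10.2 counts a missing relapse response as a relapse, and SAP 8.3 imputes missing binary data as failure.

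**Conclusion.** The row is wrong as written, and the matter is minor. Followed literally, it omits the CMH tests of one secondary endpoint at 2 of 6 post-baseline visits, Weeks 20 and 24. This rests on the text alone; no assumption about relapse rates, sample size or dropout enters.

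The effect stops at that endpoint. A reader might infer that late relapse goes unanalysed. It does not: the primary time-to-relapse analysis follows subjects to Week 24 and includes the same IGA criterion, and maintained IGA success is tested at Weeks 20 and 24. Nothing suggests the visits were left out on purpose; a drafting omission is the likeliest explanation.

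**What to change.** Add Week 20 and Week 24 to the visit cell for the IGA increase of at least 2 points in the SAP 10.2 table. Do this before any unblinding, including for the interim analysis that SAP 2.2 allows. If a stop at Week 16 was in fact intended, SAP Section 14 should state and justify it, and SAP 5.2 and the row title should be changed to match.

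The cost is one table cell. No new data are needed, since IGA is already collected and windowed at both visits.

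As an optional editorial change, the imputed repeat could be called missing as relapse for the two worsening endpoints in SAP 10.2.1, 10.2.2 and the output titles, to match SAP 10.2.
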